9.3. Interim and final statistical analyses

The primary endpoint is the distribution of scores on the modified Rankin Scale (mRS) at day 90. We will test the primary efficacy and futility hypotheses at the interim and final analysis using the generalized likelihood ratio (GLR) test, based on whether the usual normal approximation to the Wilcoxon-Mann-Whitney test statistic crosses a futility or efficacy boundary at interim or final analysis. The primary analysis will be conducted in the adaptive design sample (see section 5.2 for definition), according to the intention to treat principle, adjusted for the adaptive design, and unadjusted for covariates. See Appendix 2 for detailed specification of the interim and final calculations.

The efficacy bounds at interim and final analysis are set to control the overall (one-sided) Type I error rate at 2.5%. There are three group sequential boundaries: an interim futility boundary b_f , an interim efficacy boundary b_e , and a final efficacy bound c , which are fixed before the first interim analysis. At each of the two interim analyses, the futility bound b_f is used to decide if the study should continue recruitment in the overall group, shift accrual and testing to a subgroup, or stop in its entirety. The futility boundary takes into account the fact that the maximum analyzed sample size is a random variable that is no larger than the fixed maximum number of subjects randomized ($n=476$). Because subgroup selection reduces the maximum number of subjects available for analysis at completion of the study, this method effectively allows an easier futility stop after subgroup selection. This setup replaces conditional power analyses with an automatic and more efficient adjustment of boundaries.

If the patients are equally distributed across the six cells, the efficacy boundary at the interim analyses will be 2.62, the efficacy boundary at the final analysis will be 2.61, and the futility boundary at the interim analyses will be 1.88. If the patients are not distributed equally, these boundaries will be adapted slightly.²

First interim analysis (based on primary outcome data obtained from the first 200 consecutively randomized subjects)

The null hypothesis is tested in the entire subject population, and, depending on the results:

1. If neither efficacy nor futility bound is crossed, the trial continues with enrollment in the overall population to the 2nd-interim analysis.
2. If the efficacy bound is crossed, the trial stops and efficacy is declared in the overall population.
3. If the futility bound is crossed, the optimal subgroup is selected based on the Kullback-Leibler criterion and the null is tested in that subgroup.
 - 3.1. If neither bound is crossed, the trial will continue with enrollment limited to the selected subgroup.
 - 3.2. If the efficacy bound is crossed, the trial stops and efficacy is declared in the selected subgroup
 - 3.3. If the futility bound is crossed, the trial stops for futility.

Second interim analysis (after primary outcome data obtained from an additional 140 consecutively randomized subjects within the target population defined by the first interim analysis)

If, after the first interim analysis, the study proceeds with enrollment in the overall population (option 1, under first interim analysis), the testing at the 2nd-interim analysis is identical to the first interim and the decisions to stop or proceed with enrollment are identical to those outlined above under the first interim analysis.

If, after the first interim analysis, enrollment is limited to a selected subgroup (option 3, under first interim analysis), the second interim analysis is based on a test of the null hypothesis in the selected subgroup only and, depending on the results:

1. If neither bound is crossed, the trial continues to the final analysis with enrollment of additional subjects limited to the selected subgroup
2. If the efficacy bound is crossed, the trial stops and efficacy is declared in the selected subgroup
3. If the futility bound is crossed, the trial stops for futility. Note that there is no option for "second subgroup selection".

Final analysis (after primary outcome data obtained from an additional 136 consecutively randomized subjects within the target population defined by the second interim analysis)

If, after the second interim analysis, the study proceeds with enrollment in the overall population the null is tested in the overall population, and, depending on the results:

1. If the efficacy bound is crossed, endovascular therapy is declared efficacious in the overall population.
2. If the efficacy bound is not crossed, the optimal subgroup is selected and the null is tested in that group:
 - 2.1. If the efficacy bound is crossed, endovascular therapy is declared efficacious in that subgroup
 - 2.2. If the efficacy bound is not crossed, endovascular therapy will be declared of no benefit.

~~If enrollment after one of the interim analyses is limited to a selected subgroup, then at the final analysis the null will be tested in that subgroup only and efficacy or lack thereof will be declared as per options 2.1 and 2.2 above.~~

~~The computation of the test statistics and the Kullback-Leibler selection criterion are specified in Appendix 2. Calculation of the test statistics will be carried out in SAS by the NDMC. A more detailed description of the adaptive design is provided in Appendix 3.~~

9.4. Interim and Final statistical analysis

The overall null hypothesis for the primary endpoint will be tested using the Wilcoxon rank sum statistic and asymptotic pvalue generated via the NPAR1WAY procedure in SAS. Tied values will be assigned the average rank for the corresponding value, as is the default. The continuity correction will not be applied.

Based on external information generated from the DAWN trial, an early interim analysis was requested by NINDS in order to make a determination as to whether DEFUSE should continue in the original population or a subpopulation or be terminated early. For the early interim analysis, the efficacy hypothesis will be tested at the one-sided Type 1 error probability of 0.023. The 90-day mRS for subjects who have not yet reached the end of the study protocol will be imputed with their respective 30-day mRS. Subjects with no 30-day or 90-day mRS scores will be excluded. The DSMB will be provided with the results of this analysis and would likely recommend stopping the study if the result is significant at the one-sided 0.023 level. Subsequently, upon submission of the last-randomized subject's 90-day outcome data into the WebDCU™ (anticipated in mid-August 2017) and the database lock, the analysis will be repeated at the one-sided alpha level of 0.023. The manuscript for the DEFUSE 3 Trial results will ~~reflect~~ contain results from this second analysis executed on the final locked database.

If the interim analysis is not significant at the one-sided alpha level of 0.023, it is anticipated that the DSMB will review the results and may request any additional subgroup analyses in order to make recommendations to NINDS. Such requests will be documented in an addendum to the SAP. Following the DSMB review and recommendation, the NINDS may make the decision to continue the study with recruitment of the DEFUSE 3 eligible patients per the current eligibility criteria, and the study may continue per the current protocol. In this case, the final primary outcome analysis will be tested at the one-sided alpha=0.001 (which will be referred to as "alpha2"). If the decision is made to terminate the study, upon submission of the last-randomized subject's 90-day outcome data into the WebDCU™ (anticipated in mid-August 2017) and the database locked, the analysis will be repeated at the one-sided alpha level of 0.023.

The NINDS may also direct the study team to continue the study in a subset of the current DEFUSE 3 eligible patient population (such as DAWN-ineligible patients). If this is deemed feasible, then the final analysis will include all patients enrolled (both before and after the subset selection was imposed) and will be evaluated with a one-sided alpha of 0.001 (which will be referred to as alpha3).

The rationale for recommending the extreme split of the alpha is that:

(a) given the conditions currently imposed by the CIRB (i.e., recruit only DAWN-ineligible patients), continuing the DEFUSE 3 study with the current eligibility criteria is unlikely to be

feasible; and (b) the sites have reported significant concerns regarding recruiting the DAWN-ineligible patients due to its complex definition.

To date, the DEFUSE 3 Executive Committee has proposed and DSMB had effectively recommended $\alpha_2 + \alpha_3 = 0$, since they do not envision any circumstance where continuation of DEFUSE 3 in its current form is feasible. If a continuation is requested by the NINDS, a sample size will need to be reassessed based on the desired effect in the modified study population and the one-sided α_2/α_3 required for efficacy. This evaluation will likely result in increased total sample size for the study.

9.5. Reporting of primary results

The results of the study will be primarily expressed as whether or not an efficacy boundary was crossed at ~~either one of the two interim analyses or at the final analysis. The efficacy boundary is set, a priori, to guarantee less than a 2.5% one-sided error rate.~~ Crossing of the efficacy boundary will be considered evidence that endovascular therapy is beneficial, based on lower day-90 mRS scores in the endovascular group compared to controls.

9.6. Estimation of p-values, effect size estimates, and CIs after trial completion

The treatment effect will be ~~adjusted for study design and~~ expressed as

- The common odds ratio with its 95% confidence interval and p-value, calculated using a proportional odds model.
- The average number needed to treat for benefit (NNT), with its 95% confidence interval, where $NNT = 1 / (P_EndovascularSuperior - P_MedicalSuperior)$.⁴

10. Sample size determination for primary efficacy analysis

The sample size determination begins with a preliminary estimate of the effect size that is plausible to expect and which is also clinically meaningful. Fixing standard operating characteristics at 5% two-sided Type 1 error and 10% Type 2 error (90% power) leads to a sample size lower bound for a hypothetical fixed-sample trial with no adaptation and no interim analysis. We then adjust the sample size for the group-sequential modification and the subgroup adaptive design.

The projected overall effect of endovascular therapy is based on 1) the observed 90-day modified Rankin Scale outcomes in DEFUSE 2 of target mismatch patients treated >6hrs after symptom onset and 2) the assumption that early reperfusion will be achieved in 75% of the endovascular arm vs. 20% of the medical therapy arm.⁵⁻⁷ Using these data, we have projected the distributions on the mRS at 90 days for subjects in the endovascular and control arms of DEFUSE 3. (Table 1)

	mRS at day 90							Total
	0	1	2	3	4	5	6	
Endovascular group	18.0%	11.5%	19.6%	11.5%	16.4%	11.5%	11.5%	100%
Medical group	9.7%	7.9%	15.0%	17.7%	14.4%	17.7%	17.7%	100%

Table 1. Projected 90-day mRS distributions in DEFUSE 3

These distributions correspond to a standardized effect of 0.36 for the primary analysis. Based on these data, the fixed sample size for a non-adaptive design requires 376 patients (188 per arm) to have 90% power at an alpha of 5% (Wilcoxon-Mann-Whitney test); 100 patients were

added for the adaptive design to reach a maximum sample size of 476 for DEFUSE 3. The size of this increase is based on simulations and is selected to preserve the desired operating characteristics, while allowing shrinkage in effect size to 0.30, since the above estimate of 0.36 may be optimistic. The sample size of 476 is also the largest sample that can be accrued within budget and time limitations.

Simulations (n=5000) are used to compare the performance of a traditional fixed sample size design (fixed n=476) to the adaptive design (max randomized n=476) under the null and various alternative scenarios (**Table 2**). For the simulations the effect size is expressed as a standardized effect *in the disjoint cells*, which are cumulated to form the subgroups as described above, where a standardized effect of 0.3 corresponds to a conservative projected effect of endovascular therapy (anticipated effect 0.36; see above).

Sim.	Standardized effect in cells*						Average standard effect	Adaptive Design		Fixed-Design	
	C ₁₁	C ₂₁	C ₁₂	C ₂₂	C ₁₃	C ₂₃		Average No. randomized	Power	Number randomized	Power
#0	0	0	0	0	0	0	0	361	2.2%	476	2.5%
#1	0.3	0.3	0.3	0.3	0.3	0.3	0.3	354	80%	476	89%
#2	0.5	0.4	0.3	0	0	0	0.2	400	86%	476	55%
#3	0.5	0.5	0	0	0	0	0.17	403	87%	476	41%

Table 2. Simulations comparing the adaptive and the fixed trial designs. *Cells are defined in figure 1. Under the null (scenario #0), the adaptive design controls the total Type 1 error below 2.5%, stops early for futility 63% of the time, and the average number of randomizations is 361. If the effect is uniform across cells—and therefore also over cumulated subgroups—(scenario #2), the fixed sample design is optimal, but the adaptive design results in only a small loss of power (from 89 to 80%). When the effect size distribution across the subgroups is in accord with the biological assumptions (scenarios #2 and 3), so that the effect in the cumulated subgroups declines as more cells with a null effect are added in, the adaptive design performs much better (higher power and smaller expected sample size) than the fixed sample, conventional trial. The adaptive design also performs well compared to a non-adaptive, fixed sample that includes efficient multiple comparisons-adjusted testing for effect in subgroups at the end of the study.²⁻ Note that in all of the tabulated examples (other than the first, which is the null case), the overall population null is false, because the effect is positive in some cell or cells, and the effect is null in the others, so that the effect never becomes negative. If we allow negative effects in any of the cells, then the advantages of the adaptive design over the conventional design grow even larger.

11. Exploratory analyses of the primary outcome after trial completion

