This distribution corresponds to a standardized effect of 0.36 for the primary analysis. Based on these data, the fixed sample size for a non-adaptive design requires a total of 376 patients (188/arm) to have 90% power at an alpha of 5% (Wilcoxon-Mann-Whitney test); 100 additional patients are added for the adaptive design to reach a maximum sample size of 476 for DEFUSE 3.

We ran simulations (n=5000) to compare the performance of a traditional fixed sample-size design (fixed n=476) to the adaptive design (max n=476) under various scenarios (see **Table 3**, below). For the simulations the effect size is expressed as a standardized effect, where a standardized effect of 0.3 corresponds to a conservative projected effect of endovascular therapy (anticipated effect 0.36; see above).

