Table 3. Under the null (Scenario #0), the adaptive design controls the total Type 1 error below 2.5%, stops early for futility 63% of the time, and the average number of randomizations is 361. If the effect is uniform across cells (scenario #1), the fixed-sample design is optimal, but the adaptive design results in only a small loss of power (from 89 to 80%). The adaptive design performs much better (higher power and smaller expected sample size) than the fixed sample, conventional trial when the effect size distribution across the subgroups is in accord with the biological assumptions (scenarios #2 and 3). If the effect is concentrated in two cells with small core volumes (scenario #3), the adaptive design maintains power (87%) while the conventional design collapses (41% power). The adaptive design also performs well compared to a non-adaptive, fixed sample that includes efficient multiple comparisons-adjusted testing for effect in subgroups at the end of the study. (see Lai et al⁵⁹)

Secondary analysis: Our secondary endpoint is the proportion of patients with mRS 0-2 at day 90 (indicating functional independence). The difference in the proportions of patients with mRS 0-2 between treatment arms will be assessed using logistic regression.

Subgroup analyses: Subgroup analyses of the effect of endovascular therapy on the primary and secondary endpoints will be performed. Subgroups will be defined based on the stratification variables, key demographic factors (such as race and ethnicity), tPA vs. no tPA, CTP vs. MRI selection, and witnessed vs. unwitnessed symptom onset, wake-up vs non-wake-up stroke, and TIC1 0-2a vs. TIC1 2b/3 results in cath lab.

Missing data/lost to follow-up (LTFU):

All effort is put forth to ensure near complete follow-up, in particular with the assessment of the primary outcome (mRS at 90 days), death (mRS=6), and stroke recurrence. If the primary outcome (mRS at 90 days) cannot be assessed in the clinic, it will instead be obtained by phone using a structured interview. If the subject’s mRS cannot be obtained in clinic or by phone within the window of 60 to 120 days from randomization, then for primary analyses the day 30 mRS score will be used as the primary outcome (ie day 30 mRS carried forward). If neither the 30-day nor the 90-day mRS is available, then the mRS will be imputed. We do not expect this to alter the main study results given our estimated very low LTFU rate (<2%).

DEFUSE 3 Timetable

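### SAP Section 10 sets 90% power and says the added 100 patients preserve it at an effect of 0.30, but Table 2 shows 80%; the caption names the wrong scenario and 0.36 does not follow from Table 1

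*SAP*

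**What the plan says.** SAP Section 10 starts from a hypothetical trial without adaptation or interim looks: "Fixing standard operating characteristics at 5% two-sided Type 1 error and 10% Type 2 error (90% power"). From the projected mRS distributions in its Table 1 it obtains 376 patients (188 per arm) and says of those distributions: "These distributions correspond to a standardized effect of 0.36 for the primary analysis". Protocol 3.8 says the same: "This distribution corresponds to a standardized effect of 0.36 for the primary analysis".

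A further 100 patients bring the maximum to 476. Section 10 says the size of this increase was "selected to preserve the desired operating characteristics, while allowing shrinkage in effect size to 0.30", because 0.36 might be optimistic. It adds a second reason: "The sample size of 476 is also the largest sample that can be accrued within budget and time limitations".

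The text introducing Table 2 calls 0.30 the conservative effect and sets it beside the "anticipated effect 0.36; see above". The relevant entries of Table 2 are:

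| Scenario | Cell effects | Adaptive power | Fixed 476 power |
|---|---|---|---|
| #0 | all 0 | 2.2% | 2.5% |
| #1 | all 0.30 | 80% | 89% |
| #2 | 0.5, 0.4, 0.3, 0, 0, 0 | 86% | 55% |
| #3 | 0.5, 0.5, 0, 0, 0, 0 | 87% | 41% |

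For the uniform effect, the SAP caption reads "scenario #2), the fixed sample design is optimal, but the adaptive design results in only a small loss of power (from 89 to 80"%). The protocol's caption to the same table reads "If the effect is uniform across cells (scenario #1), the fixed-sample design is optimal".

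**The concern.** Three statements in one short section do not fit together.

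- The only power figure set as a target is 90%. The text says the desired characteristics hold down to 0.30, and the table beneath shows 80% there for the design actually planned.
- The caption points to a row that is not uniform and does not contain the figures it cites.
- The effect of 0.36 opens the argument, and 0.30 is presented as a cautious discount from it. If the two numbers are on different scales, or 0.36 is too high, the discount is smaller than it looks.

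At stake is whether a reader can tell which power the extra 100 patients were meant to secure, and how much optimism the design could absorb.

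**Working it through.** **1. Reproduce the 376.** Inputs: Table 1 of SAP Section 10, with the medical row (which sums to 100.1%) rescaled; two-sided 5%, 90% power, 1:1 allocation.

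- P(endovascular better) = 0.5251, P(worse) = 0.3345, P(tie) = 0.1405.
- P(better) + ½ P(tie) = 0.5953; excess over one half = 0.0953.
- Tie factor = 1 − Σ(pooled proportion)³ = 0.9783.
- Effect on the tie-corrected rank scale = 0.0953 × √(12/0.9783) = 0.334.
- Total N = 4 × (1.960 + 1.282)² / 0.334² ≈ 377.

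Simulated Wilcoxon power at 188 per arm is 90.4%. The 376 stands.

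**2. Try to reproduce 0.36 from the same table.**

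| Scale | Effect |
|---|---|
| Tie-corrected rank | 0.334 |
| Mean difference / pooled SD | 0.340 |
| √2 × probit of 0.5953 | 0.341 |
| Ordered probit | 0.349 |
| Mean of the six cumulative probit shifts | 0.351 |
| Common log odds ratio 0.591 × √3/π | 0.326 |
| Rank effect with ties discarded | 0.398 |

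None gives 0.36.

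**3. Find the scale of Table 2.** Wilcoxon tests on unit-variance normal shifts, fixed 476, one-sided 2.5%, equal cells, give 89.1%, 56.0% and 41.2% for scenarios #1 to #3. Table 2 prints 89%, 55% and 41%. So Table 2's fixed column behaves as a normal-shift scale. On that scale Table 1 corresponds to about 0.341 to 0.351.

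**4. Test whether one conversion fits both printed pairs** (0.36 with 376 patients at 90%; 0.30 with 476 at 89%). With relative efficiency e, N = 4 × 10.507 / (e × effect²) and power = Φ(effect × √(eN/4) − 1.96).

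- e = 0.864: 0.36 needs N = 375.4, or 188 per arm. But 476 at 0.30 gives Φ(3.042 − 1.96) = 86.0%, not 89%. The Monte Carlo standard error of 89% from 5,000 runs is √(0.89 × 0.11/5000) = 0.44 points, so this is not simulation noise.
- e = 0.955 (Wilcoxon under normal shifts): 476 at 0.30 gives Φ(3.198 − 1.96) = 89.2%, which matches. But 376 at 0.36 would have about 92-93% (simulated 92.4%), and the effect that goes with 376 at 90% is 0.342.

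Neither conversion fits both.

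**5. Allowance for optimism, like for like.**

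- As printed: 1 − 0.30/0.36 = 16.7%.
- Normal-shift scale: 1 − 0.30/0.341 = 12.0%; 1 − 0.30/0.349 = 14.0%; 1 − 0.30/0.351 = 14.5%.
- Rank scale: a normal shift of 0.30 becomes √12 × (Φ(0.30/√2) − 0.5) = 0.291, and 1 − 0.291/0.334 = 12.8%.

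**6. Power at 0.30.** Table 2 gives 80% for the adaptive design, 10 points below the 90% set in the section. On the scale that matches Table 2, a fixed trial alone would need 4 × 10.507 / (0.955 × 0.09) = 489, rounded up to 490 in two equal arms. So 476 cannot give 90% at 0.30 even without adaptation, as the printed 89% shows.

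**7. Caption.** Only row #1 is uniform, and only row #1 contains 89% and 80%. The SAP caption's next sentence uses scenarios #2 and #3 for the non-uniform cases, so #2 is described in both ways.

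**The case against.** The strongest reply has four parts.

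- *Nothing is hidden.* Section 10 states 5% error and 90% power, formally for the fixed-sample bound, and prints the adaptive 80% directly below. This stands. A reader might infer that the target is missing altogether or that the shortfall is concealed; the documents support neither. What is left open is only whether the 90% was meant to carry over to the adaptive design at 0.30.
- *The 376 was derived from the distributions, not from 0.36.* This also stands. A reader might infer from step 2 that 376 is wrong and the trial undersized; step 1 rules that out. It matters because the DSMB later used 376 for its boundary (182/376 = 0.48, the information fraction in the July 24 memorandum).
- *The scale may be defined elsewhere.* The struck-out part of SAP 9.3 refers to Appendices 2 and 3, and Section 10 cites the adaptive-design paper; none is in the text provided. So the claim is limited to that text. Even so, 0.36 and 0.30 are set side by side as if comparable, and step 4 finds no conversion that makes them so.
- *The caption corrects itself and the design is gone.* The slip is easy to spot, and SAP Section 2 withdrew the adaptive interim analyses. That limits the consequence but not the error: Section 2 deletes Sections 9.2-9.4 of the prior SAP, not Section 10.

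It is also tempting to compare 0.334, or the log-odds value 0.326, directly with 0.30 and report a discount of only 8-10%. That mixes scales; the consistent figure is about 12-15%.

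**Conclusion.** Section 10 needs three corrections as written. Type 1 error is preserved (2.2%, under the 2.5% one-sided limit), but at a uniform 0.30 the adaptive design has 80% power, not the 90% that the section sets. The SAP caption should name scenario #1. The effect of 0.36 is too high for Table 1 or is on a scale not matched to Table 2's 0.30; the values are about 0.34-0.35 on the normal-shift scale and 0.334 on the rank scale. The room for optimism is about 12-15%, not 17%.

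The size is minor. The 376 is right, the 476 also rests on a stated budget and time limit, and no sample size, boundary or test changes. The caption error is certain. The power statement rests on Table 2 as printed, because the adaptive 80% cannot be recomputed exactly without the appendices. The scale finding assumes Table 1 as printed (medical row rescaled) and infers Table 2's scale from its fixed-design column.

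**What to change.** (a) SAP Section 10: replace the sentence on preserved operating characteristics with Table 2's figures, for example: *With a maximum of 476, simulations give the adaptive design a one-sided type 1 error of 2.2%, 80% power at a uniform effect of 0.30 (scenario #1) and 86-87% in scenarios #2 and #3; a fixed trial of 476 has 89% at 0.30.* Keep the sentence on budget and time.

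(b) SAP Table 2 caption: for the uniform effect, change scenario #2 to scenario #1.

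(c) Protocol 3.8 and SAP Section 10, wherever 0.36 appears: restate it on the scale of Table 2's 0.30 (about 0.34 on the normal-shift scale). If the rank scale is preferred, give about 0.33 against 0.29. Otherwise state the scale on which the effect is 0.36 and convert 0.30 to it.

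The cost is wording in two sections: no added patients and no change to any analysis. The stated justification becomes slightly less favourable.
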